## 5.4 Prior and Concomitant Therapy

---

If a subject reports taking any over-the-counter or prescription medications, vitamins, and/or herbal supplements, or if administration of any medication becomes necessary, beginning with the screening visit through the end of the study, the name of the medication, dosage information including dose, route and frequency, date(s) of administration including start and end dates, and reason for use must be recorded. Although cautionary, use of strong or moderate CYP3A inhibitors or moderate inducers, or P-gp substrates or inhibitors are allowed if no appropriate therapeutic alternative exists (refer to the Operations Manual, Section 3.3). Concomitant use of a moderate CYP3A inducer should be avoided. Alternative treatments with less CYP3A induction or inhibition should be considered. Concomitant use of a P-gp substrate should be avoided. Alternative treatments should be considered. If use of P-gp substrate is unavoidable, P-gp substrate should be separately dosed at least 6 hours before venetoclax. Herbal supplements known to inhibit or induce CYP3A or P-glycoprotein (P-gp) should be excluded and use of other supplements should be discouraged. Transfusion of blood and blood products, antibiotics, anti-fungals, anti-emetics, granulocyte-colony stimulating factor (G-CSF), and other standard supportive care medications are permitted as needed, per institutional practices. Anti-uric acid agents (such as hydroxyurea or allopurinol) or leukapheresis are also permitted per institutional guidelines and to decrease WBC counts to  $< 25 \times 10^9/L$  at the time of study entry or during the study, as needed.

Filgrastim may be administered, per clinical practice.

Venetoclax dose modifications for co-administration with strong or moderate CYP3A inhibitors and P-gp inhibitors during Cycle 1 and after ramp-up are noted below and in [Table 1](#). Two to three days post the removal of the strong or moderate CYP3A inhibitor or P-gp inhibitor, venetoclax treatment will be given at the target dose of 400 mg without the need to ramp-up.

- For subjects who are on a strong CYP3A inhibitor, at the time of initiation, the dose of venetoclax will be reduced ([Table 1](#)) for the duration of treatment with the strong CYP3A inhibitor.

- For subjects who are on posaconazole, at the time of initiation, the dose of venetoclax will be reduced ([Table 1](#)) for the duration of treatment with posaconazole.

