- For subjects who are on a moderate CYP3A inhibitor (such as ciprofloxacin, fluconazole or isavuconazole) or a P-gp inhibitor (such as amiodarone or captopril), the venetoclax dose will be reduced by 50% ([Table 1](#)) for the duration of treatment with the moderate CYP3A inhibitor or P-gp inhibitor.

**Table 1. Dose Modification for Venetoclax When Co-administered with P-gp Inhibitors or Moderate or Strong CYP3A Inhibitors**

Venetoclax Dose (mg) a	Venetoclax Dose if Co-Administered with 1 or more Strong CYP3A Inhibitor	Venetoclax Dose if Co-Administered with posaconazole	Venetoclax Dose if Co-Administered with 1 or more Moderate CYP3A Inhibitor or P-gp Inhibitor
100 mg (Cycle 1 Day 1 only)	10 mg	10 mg	50 mg
200 mg (Cycle 1 Day 2 only)	20 mg	20 mg	100 mg
400 mg (Cycle 1 Day 3)	50 mg	50 mg	200 mg
400 mg (Cycle 1 Day 4 and daily thereafter)	100 mg	70 mg	200 mg
400 mg (Target Dose after Ramp-up)	100 mg	70 mg	200 mg

CYP3A = Cytochrome P450 3A; P-gp = P glycoprotein

a. If a subject requires co-administration of venetoclax with both a strong and a moderate CYP3A inhibitor or a P-gp inhibitor, venetoclax dose modification recommended for strong CYP3A inhibitors should be followed.

Any questions regarding concomitant or prior therapy should be raised to the AbbVie emergency contact. Information regarding potential drug interactions with venetoclax (ABT-199) can be located in the Venetoclax Investigator's Brochure. A sample list of excluded and cautionary medications is provided in [Appendix D](#).

If a CYP3A inhibitor or P-gp inhibitor is discontinued, resume the venetoclax target dose 2 to 3 days after discontinuation of the inhibitor.

Subjects must be able to safely discontinue any prohibited medications 4 weeks prior to first dose of study drug administration. Subjects must be consented for the study prior to discontinuing any prohibited medications for the purpose of meeting study eligibility.

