## APPENDIX D. SAMPLE LIST OF EXCLUDED AND CAUTIONARY MEDICATIONS, WITH ADDITIONAL GUIDANCE NOTED

Excluded
Strong CYP3A inducers – avasimibe, carbamazepine, enzalutamine, mitotane, phenytoin, rifampin, St. John's wort
Cautionary, Additional Guidance Noted ^
Moderate CYP3A inducers – bosentan, efavirenz, etravirine, modafinil, nafcillin
Strong CYP3A inhibitors – boceprevir, clarithromycin, cobicistat, conivaptan, danoprevir/ritonavir, elvitegravir/ritonavir, idelalisib,* indinavir, itraconazole, ketoconazole, lopinavir/ritonavir, mibefradil, nefazodone, neflfinavir, paritaprevir/ritonavir combinations, posaconazole, ritonavir, saquinavir, telaprevir, telithromycin, tipranavir/ritonavir, voriconazole
Moderate CYP3A inhibitors – amprenavir, aprepitant, atazanavir, cimetidine, ciprofloxacin, clotrimazole, crizotinib,* cyclosporine,* darunavir/ritonavir, diltiazem, dronedarone, erythromycin, fluconazole, fluvoxamine, fosamprenavir, imatinib,* isavuconazole, tofisopam, verapamil
P-gp substrates – aliskiren, ambrisentan, colchicine, dabigatran etexilate, digoxin, everolimus,* fexofenadine, lapatinib,* loperamide, maraviroc, nilotinib,* ranolazine, saxagliptin, sirolimus,* sitagliptin, talinolol, tolvaptan, topotecan*
P-gp inhibitors – amiodarone, captopril, carvedilol, felodipine, quercetin, quinidine, ranolazine, ticagrelor
Cautionary
Warfarin and Coumarin Derivatives (e.g., phenprocoumon)**
BCRP substrates – methotrexate,* mitoxantrone,* irinotecan,* lapatinib,* rosuvastatin, sulfasalazine, topotecan*
OATP1B1/1B3 substrates – atrasentan, atorvastatin, ezetimibe, fluvastatin, glyburide, rosuvastatin, pitavastatin, pravastatin, repaglinide, simvastatin acid, telmisartan, valsartan, olmesartan
BCRP inhibitors – geftinib*

Note that this is not an exhaustive list. For an updated list, see the following link:

<https://www.fda.gov/Drugs/DevelopmentApprovalProcess/DevelopmentResources/DrugInteractionsLabeling/ucm080499.htm>

In addition to the medications listed in this table, subjects receiving venetoclax should not consume grapefruit, grapefruit products, Seville oranges (including marmalade containing Seville oranges) or Starfruits.

^ Avoid concomitant use with venetoclax. Alternative treatments should be considered. Refer to Protocol Section 5.3 and Section 5.4.

\* These are anticancer agents; consult contact the AbbVie medical monitor before use.

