Rx TREATMENT														
TLS Prophylaxis		✓	✓	✓	✓									
Dispense venetoclax and subject diary		✓							✓					
Dosing with venetoclax		✓	✓	✓	✓	✓	✓	✓	✓	✓	✓	✓	✓	
Collect venetoclax and subject diary									✓					✓
Dosing with azacitidine or decitabine (assigned at Cycle 1 Day 1)		✓	✓	✓	✓	✓	✓		✓	✓				
Dispense venetoclax in a 3-step ramp-up in 3 days to target dose of 400 mg/day: Day 1 – 100 mg, Day 2 – 200 mg, Day 3 – 400 mg, and then continuous throughout. If on concomitant: strong CYP3A inhibitor (Day 1 – 10 mg, Day 2 – 20 mg, Day 3 – 50 mg, Day 4 – 100 mg [70 mg, if on posaconazole]); moderate CYP3A inhibitor or P-gp inhibitor (Day 1 – 50 mg, Day 2 – 100 mg, Day 3 – 200 mg).														

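### Section 5.4 does not lead to one venetoclax dose when a subject takes two interacting inhibitors, or when one of the two is stopped

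*Protocol*

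**What the plan says.** Protocol Section 5.4 handles interacting drugs with three bullets, Table 1 with one footnote, and two sentences on what happens when an inhibitor stops.

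- **Strong-inhibitor column**, headed "Venetoclax Dose if Co-Administered with 1 or more Strong CYP3A Inhibitor": 10, 20 and 50 mg on Cycle 1 Days 1, 2 and 3, then 100 mg.
- **Posaconazole column**, headed "Venetoclax Dose if Co-Administered with posaconazole": 10, 20 and 50 mg, then 70 mg.
- **Moderate CYP3A or P-gp column**: 50, 100 and 200 mg, then 200 mg.
- **Footnote a**: "If a subject requires co-administration of venetoclax with both a strong and a moderate CYP3A inhibitor or a P-gp inhibitor", the "venetoclax dose modification recommended for strong CYP3A inhibitors should be followed". Posaconazole is not named.
- **Bullets**: there is one each for strong inhibitors, posaconazole, and moderate CYP3A or P-gp inhibitors. The second begins "For subjects who are on posaconazole, at the time of initiation, the dose of venetoclax will be reduced". Each bullet keeps its reduction for as long as that inhibitor is given, and none makes an exception for a second drug.
- **Stopping**: a sentence ahead of the bullets puts the subject on 400 mg, without a new ramp-up, two to three days after the inhibitor is removed. After Table 1 the text repeats: "If a CYP3A inhibitor or P-gp inhibitor is discontinued, resume the venetoclax target dose 2 to 3 days after discontinuation of the inhibitor".

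Three other places bear on this. Appendix D includes posaconazole in its strong CYP3A inhibitor list ("paritaprevir/ritonavir combinations, posaconazole, ritonavir"). The treatment note in Appendix H gives the strong-inhibitor schedule with 100 mg on Day 4 and adds in brackets "70 mg, if on posaconazole". The visit notes in Operations Manual Section 2.1 name posaconazole as an item separate from strong and moderate inhibitors and refer the site to Table 1.

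**The concern.** Footnote a is the only text that says what to do when inhibitors of different strength are combined. It points to a class, and the protocol places posaconazole inside that class in Appendices D and H but beside it in Table 1 and the Operations Manual. A site with a subject on posaconazole and, say, ciprofloxacin or amiodarone (both named in Section 5.4) has to decide for itself which column footnote a means.

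The stopping sentences raise a second problem, which is not limited to posaconazole. They are triggered by the end of one inhibitor and are silent about any other that continues.

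The situation is foreseeable. Sections 6.1 and 6.2 call for bacterial, viral and fungal prophylaxis, Section 5.4 gives an antibacterial and azole antifungals as examples of moderate inhibitors, and footnote a itself shows that combinations were expected. Cytopenias and TLS are the protocol's adverse events of special interest, so the dose these subjects receive should not depend on how a site parses a footnote. The SAP (Section 8.2) also summarizes dose intensity, which will reflect whichever dose was given.

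**Working it through.** No sample-size or power figure is involved. The check is to take each combination to Table 1 and count the entries that the text can support.

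**Step 1. Both inhibitors continuing, dose from Cycle 1 Day 4.**

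| Combination | Governing text | Entry |
|---|---|---|
| Two strong inhibitors, neither posaconazole | Strong column heading covers one or more | 100 mg |
| Strong (not posaconazole) + moderate or P-gp | Footnote a | 100 mg |
| Two from the moderate/P-gp group | That column's heading | 200 mg |
| Posaconazole + moderate or P-gp | Footnote a read by column heading; or the posaconazole bullet and column | 100 mg or 70 mg |
| Posaconazole + another strong inhibitor | Strong column heading; or the posaconazole bullet and column | 100 mg or 70 mg |

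The first three rows resolve to one entry. The last two do not.

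**Step 2. Size of the difference between the two readings.** On Cycle 1 Days 1 to 3 both columns give 10, 20 and 50 mg, so the difference is zero. From Day 4 it is 100 − 70 = 30 mg; 100/70 = 1.43, so the higher reading is 43% above the lower. Against the 400 mg target the readings are 100/400 = 25% and 70/400 = 17.5%.

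**Step 3. Does another passage settle it?** In Appendix H the 70 mg figure is an exception nested inside the strong-inhibitor schedule. If footnote a means that whole schedule, it leads to 70 mg. But the Appendix H note names no combination, and the Operations Manual sends the reader back to Table 1, where the two are separate columns. If posaconazole is taken to stand beside the strong class, as the Operations Manual lists it, footnote a does not cover posaconazole plus a moderate inhibitor at all. For posaconazole plus another strong inhibitor, Section 5.4 has no ranking on any reading.

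**Step 4. One of two inhibitors stops.** The stopping sentences taken alone, against the bullet and column for the inhibitor that continues:

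| Inhibitor that continues | Stopping sentences | Bullet and Table 1 | Ratio |
|---|---|---|---|
| Posaconazole | 400 mg | 70 mg | 400/70 = 5.7 |
| Another strong inhibitor | 400 mg | 100 mg | 400/100 = 4 |
| Moderate CYP3A or P-gp inhibitor | 400 mg | 200 mg | 400/200 = 2 |

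These ratios measure how far apart the literal texts lie. They are not a forecast of doses given.

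**Step 5. Reach into the analysis.** The subgroup in SAP Section 9.5 is whether CYP3A inhibitor use led to a venetoclax reduction, yes or no. Doses of 70 mg and 100 mg both count as yes, so classification does not depend on which of these two readings a site follows. The sample-size statement (60 subjects, within 13% with 95% confidence) does not use dose.

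**The case against.** The best reply is that the protocol, read as a whole, has one sensible meaning. Because Appendix D lists posaconazole as strong, posaconazole alone would fit both columns if the headings were taken literally. A separate column and bullet make sense only if the specific entry displaces the general one. Appendix H writes it exactly that way. On this view footnote a leads to 70 mg, the dose does not rise when a second inhibitor is added, and a site giving 100 mg would be departing from the posaconazole bullet. Likewise, a site giving 400 mg while posaconazole continues would breach that same bullet.

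Much of this stands. A reader might infer that the protocol expressly prescribes two doses, or that adding an inhibitor raises the dose. The documents do not support that: no passage assigns 100 mg to posaconazole plus a second drug, and Appendix H and the bullet favor 70 mg. What the reply does not do is put the answer where the site will look. Footnote a and Table 1 do not state the exception, posaconazole plus another strong inhibitor is not addressed, and Appendix H says nothing about stopping. The stopping sentences can be squared with the bullets only by supplying a condition that neither sentence contains.

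There are safeguards too. CYP3A and P-gp inhibitors are allowed only where no suitable alternative exists, Section 6.1 asks that interactions be considered and doses adjusted, a Day 4 dose step carries its own TLS laboratory check on Day 5, and questions go to the sponsor's emergency contact. These lower the risk, but the last works only if the site notices the ambiguity.

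**Conclusion.** The point holds as an unresolved dosing instruction with two parts. Posaconazole with a second inhibitor can be read as 100 mg or 70 mg from Cycle 1 Day 4, with the weight of the text on 70 mg but no statement to that effect in Section 5.4. And for any subject on two inhibitors, the stopping sentences conflict, on their literal wording, with the bullets that keep the continuing inhibitor's reduction in force. The second part is wider in reach and the texts lie further apart there (2- to 5.7-fold, against 1.43-fold).

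This rests on the current wording alone and implies no view on which dose is right.

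Two larger inferences should be resisted. The first is a count of affected subjects. The only related figure is from the low-dose cytarabine study in Section 2.1, where 40% took moderate and 7% strong CYP3A inhibitors for at least 7 days. That study at first prohibited both classes, and the figure says nothing about combinations or posaconazole. The second is that the trial's results turn on this. The primary endpoint's precision statement is unaffected, and no distortion of the safety results can be shown from the documents. It still warrants correction, because it concerns the dose of a drug for which TLS and cytopenias are monitored as events of special interest.

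**What to change.** Reconcile footnote a, the Table 1 column headings, the three Section 5.4 bullets, both stopping sentences, and Appendices D and H, so that each of the following leads to exactly one Table 1 entry:

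- posaconazole with a moderate CYP3A inhibitor;
- posaconazole with a P-gp inhibitor;
- posaconazole with another strong CYP3A inhibitor;
- any two inhibitors when one is stopped and the other continues.

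Footnote a should say whether its reference to strong inhibitors includes posaconazole. The two stopping sentences should say what applies when another listed inhibitor continues, consistently with the bullets. The sponsor decides which entry applies in each case; none is proposed here.

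The cost is a reworded footnote and a sentence or two, issued as a protocol amendment or clarification letter. It needs no new data, visits or subjects, and no change to the SAP.

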## 5.5 Withdrawal of Subjects and Discontinuation of Study

Subjects will continue their treatment assignment until documented disease progression, unacceptable toxicity, withdrawal of consent, or the subject meets other protocol criteria for discontinuation (whichever occurs first). All subjects will have a Final Visit performed when treatment is discontinued unless the subject has withdrawn consent to participate in the study. A 30-day safety follow-up visit will also be conducted after the last dose of study drug. After the study period ends, subjects may continue

receiving AML-directed therapy including commercially acquired standard-of-care treatments for venetoclax and azacitidine or decitabine.

A subject may voluntarily withdraw or be withdrawn from the study at any time for reasons including, but not limited to, the following:

- Clinically significant abnormal laboratory results or adverse events, which rule out continuation of the study drug, as determined by the investigator or the AbbVie Therapeutic Area Medical Director.
- The investigator believes discontinuation is in the best interest of the subject.
- The subject requests withdrawal from the study.
- Eligibility criteria violation was noted after the subject started study drug and continuation of the study drug would place the subject at risk.
- Introduction of prohibited medications or dosages and continuation of the study drug would place the subject at risk.
- The occurrence of an adverse event that precludes further azacitidine or decitabine drug administration.
- The subject experiences toxicities related to study drug requiring more than a 4-week (1 cycle) dose interruption of venetoclax, azacitidine, or decitabine, in the absence of clinical benefit.
- The subject requires radiotherapy or alternate anti-neoplastic agents for a new primary cancer diagnosis or AML during the study period (with the exception of hydroxyurea for AML during Cycle 1 only)
- The subject becomes pregnant while on study drug.
- Subject is significantly noncompliant with study procedures, which would put the subject at risk for continued participation in the trial.

For subjects to be considered lost to follow-up, reasonable attempts must be made to obtain information on the subject's final status. At a minimum, 2 telephone calls must be made and 1 certified letter must be sent and documented in the subject's source documentation.

AbbVie may terminate this study prematurely, either in its entirety or at any site. The investigator may also stop the study at his/her site if he/she has safety concerns. If AbbVie terminates the study for safety reasons, AbbVie will promptly notify the investigator.

### **COVID-19 Pandemic-Related Acceptable Protocol Modification**

During the COVID-19 pandemic, it has been necessary to employ mitigation strategies to enable the investigator to ensure subject safety and continuity of care. Acceptable mitigation strategies are identified and included in the Operations Manual in [Appendix J](#).

The investigator should contact the sponsor medical contact before discontinuing a subject from the study for a reason other than "planned per protocol," to ensure all acceptable mitigation steps have been explored.

Refer to the Operations Manual in [Appendix J](#) for details on how to handle study activities/procedures.

## 5.6 Follow-Up for Subject Withdrawal from Study

---

To minimize missing data for effectiveness and safety assessments, subjects who prematurely discontinue study drug treatment should continue to be followed for all regularly scheduled visits, unless subjects have decided to discontinue the study participation entirely (withdrawal of informed consent). Subjects should be advised on the continued scientific importance of their data even if they discontinue treatment with study drug early.

If a subject prematurely discontinues study participation, the procedures outlined for the Final Visit should be completed as soon as possible, preferably within 2 weeks. In addition, if a subject is willing, a 30-day follow-up visit after the last dose of study drug should be completed to capture all treatment-emergent adverse events/serious adverse events have been resolved to  $\leq$  Grade 1, baseline level, or initiation of a new treatment, whichever is earlier, or, in the opinion of the investigator, the event is unlikely to resolve.

## 5.7 Study Drug

---

Venetoclax, manufactured by AbbVie, will be taken orally daily beginning on Cycle 1 Day 1, through Cycle 6 Day 28, and should be taken at approximately the same time every day for each 28-day cycle. Each dose of venetoclax should be administered with approximately 240 mL of water and within 30 minutes after the completion of breakfast or the subject's first meal of the day. On the days the subject is given either azacitidine or decitabine, venetoclax must be dosed in clinic and administered prior to these agents.

All subjects will receive a maximum of 6 cycles of venetoclax during the study period. After the study period ends, the subject may continue receiving AML-directed therapy including commercially-acquired standard-of-care treatments for venetoclax and azacitidine or decitabine.

Depending on investigator's choice, subjects will receive azacitidine or decitabine on Cycle 1 Day 1. The subject is to remain on their assigned therapy for the duration of this study. Azacitidine ( $75 \text{ mg}/\text{m}^2$ ) infusions or injections and decitabine ( $20 \text{ mg}/\text{m}^2$ ) infusions should be prepared and administered per the respective package inserts. Azacitidine will be administered SC or IV beginning on Day 1 for 7 days of each 28-day cycle, as per institutional practice. Decitabine will be administered IV beginning on Day 1 for 5 days of each 28-day cycle, as per institutional practice.

Venetoclax tablets should be swallowed whole and not chewed, crushed, or broken prior to swallowing. If a subject should forget to take his/her venetoclax dose at his/her regularly scheduled dosing time, the subject should take the forgotten dose as soon as he/she remembers, provided that the dose will be taken within 8 hours of the missed dose. Otherwise, the subject should take the next dose at the next scheduled dosing time. If the subject vomits following dosing, no additional dose should be taken that day. The next prescribed dose should be taken at the usual time.

Subject dosing will be recorded on a subject dosing diary (as described in the Operations Manual, Section 3.13). The subject will be instructed to return all study drug containers (even if empty) to the study site personnel at each study visit. The study site personnel will document compliance.

AbbVie will provide venetoclax. AbbVie provided study drug should not be substituted or alternately sourced unless otherwise directed by AbbVie. The site will be responsible for obtaining azacitidine or decitabine.

Venetoclax will be packaged in blisters or bottles with quantities sufficient to accommodate study design. Each kit will be labeled per local requirements and this label must remain affixed to the kit. Upon receipt, study drug should be stored as specified on the label and kept in a secure location. Each kit will contain a unique kit number. This kit number is assigned to a subject via interactive response technology (IRT) and encodes the appropriate study drug to be dispensed at the subject's corresponding study visit. Site staff will complete all blank spaces on the label before dispensing to subjects. Study drug will only be used for the conduct of this study.

Study drug information is presented in [Table 2](#).

